3.7 Timing of Interim and Final Analysis

Interim analysis

It will not be performed, see section 3.6.

Final analysis

Final analyses are planned to occur after March 2023. We are expecting data lock for the primary and some of the secondary hypotheses by end of March 2024. Follow up data is expected by end of June 2026. Consequently, data analysis for the first phase is expected to commence in April 2024, and for the second phase (follow-up secondary outcomes) in July 2026. The analysis database is constructed using all enrolled and consented infants.

4 Statistical Principles

4.1 Modeling Process

For the primary outcome (H1), linear mixed model with site as random effect and intervention as a fixed effect will be used.

For safety outcomes, binomial proportions and their corresponding 95% CI by intervention arm for seizure (clinical and EEG), excessive stool output, respiratory disturbances, and feeding intolerance will be reported. Chi-square/Fisher exact tests will be used to compare between the intervention arms. If we end up with a very small number of adverse events and severe adverse events, analysis of these measures will be descriptive only.

For the secondary linear outcomes (H2, H3, H5 & H12d), linear mixed model with site as random effect will be used. For secondary binary outcomes (H4, H6), generalized linear mixed model with site as random effect will be used. For count outcomes (H12a-12c), generalized linear mixed models using either Poisson or negative binomial distribution and site as random effect will be used. Intervention will be included in the models as a fixed effect. Secondary outcome models will be adjusted for breastfeeding status, maternal treatment, and stabilization dose.

Hypotheses H9 – H11 will be analyzed in a similar manner to H2. For the PROMIS model (H10), we will adjust for 1-month after discharge and if mother is the primary care giver as fixed effect covariates.

Hypothesis H8 will be analyzed using latent profile analysis as specified in Liu et al. (2). Model fit indices and likelihood ratio tests will inform the determination for the most-appropriate number of classes.

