5.1.4. Analysis of the Primary Hypothesis and Outcome

We will determine the outcome of the primary hypothesis on an intention to treat basis. We will assign infants who exit the intervention at 35 days of methadone/morphine treatment either as 35 days of opioid treatment or we will treat them as a censored value at 35 days. We will determine intervention differences of two means by analyzing the average number of days of opioid treatment from the first

weaning dose to cessation of opioid treatment. We will analyze the data using regression models that will include the intervention as a fixed effect and will include maternal treatment and stabilization dose as covariates. We will include site (hospital) in the model as a random effect. The primary test of interest will be the F-test of the intervention effect, and we will report the intervention difference along with 95% confidence interval (CI).

Because of possible censoring and removal of participants due to intervention failure, we will conduct sensitivity analysis of the primary outcome using several methods. The first sensitivity analysis will replicate the analysis, described above, and include other covariates in the model that were significantly different across the two weaning intervention groups. Sensitivity analyses will also be conducted to evaluate the effects of infants who were and were not part of the Eat Sleep Console trial as a covariate or effect modifier (see **Section 5.2.2**). Another possible sensitivity analysis will include non-parametric and/or survival regression (e.g., negative binomial, median regression, or survival analyses), as there is potential for skewness and censoring in the primary outcome.

Finally, sensitivity analysis will include fitting a competing risks model to the data where the possible competing risk states are weaned, parental withdrawal, physician withdrawal, and treatment failure (unable to wean by 35 days of methadone/morphine treatment). We will fit Cox proportional hazards models to the data to estimate the intervention effect and other covariate effects on “cause-specific hazards.” The analysis of the “cause-specific hazards” will allow for additional inquiry into the intervention effect on the primary outcome while accounting for competing safety and withdrawal risks.

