5.1.6. Bayesian Analyses

Other randomized trials of NOWS have ended prior to meeting the projected enrollment, indicating the challenges in studying this population (15, 17, and 18). In case of insufficient enrollment, we will pre-specify Bayesian analyses of the final data in addition to the frequentist analyses, defined above. Below, we first define the Bayesian analyses that will mirror the above defined frequentist analyses of the primary outcome.

We will analyze the primary outcome with a linear regression that will include treatment group (intervention arms), stabilization dose and maternal treatment as covariates, and we will include hospital as a random effect. We will use a neutral prior for treatment effect that is centered at a mean difference of 0 and a standard deviation of three, normal ($\mu=0$, $\sigma=3$) distribution. For the intercept term, we will use a normal ($\mu=0$, $\sigma=10$) prior. For all other baseline covariates in the model, we will use weakly informative neutral normal ($\mu=0$, $\sigma=2$) priors. We will use a weakly informative half-normal ($\mu=0$, $\sigma=1$) prior for the standard deviation of the random hospital effect. For all models, we will report posterior medians and 95% credible intervals (CrI) for the group mean differences and the probability that a rapid-wean intervention will reduce the days of opioid treatment, compared to a slow-wean intervention. For sensitivity analyses, we will analyze the primary outcome with skeptical and enthusiastic priors. We will center the skeptical prior at a mean difference of two, indicating the view of a skeptic with belief that the study intervention will increase the number of days of opioid treatment by two days. We will center the enthusiastic prior at a mean difference of -2, meaning a priori that an enthusiast expects the study intervention to reduce the number of days of opioid treatment by two days. In both the enthusiastic and skeptic priors, the standard deviation will be three. As with the primary frequentist analysis, sensitivity analyses may be done using Bayesian analyses, where normal ($\mu=0$, $\sigma=2$) priors will be placed on all covariates.

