6.4 Frequentist Statistical Methods

6.4.1 Statistical Methods

The proposed analyses will be conducted using the intent to treat (ITT) population.

Consort Diagram

Patient accounting will be presented in a consort diagram. This diagram will include:

- Number of infants screened
- Number of infants eligible
- Number of infants consented
- Number of infants randomized
- Number of infants randomized by group
- Number of infants in each medication category
- Number of infants with primary outcome per group per medication

Descriptive Tables

Baseline characteristics and outcomes will be descriptively summarized in the following manner:

Binary (yes/no, 1/0 type) measures will be summarized by level with frequency out of the total non-missing values and percentage of total non-missing values. Percentages will be reported to one decimal place, nn(XX.X%) or nn/NN(XX.X%)

Multiple level discrete measures will be tabulated with one row per level and with a row indicating how many observations had missing data. Percentages will be calculated as percent of all observations associated with a given treatment.

Continuous measures will be summarized by number of non-missing values, means and standard deviation [n: XX.X (XX.X)], or by median with minimum and maximum, or by median with first and third quartile [n: XX.X (XX.X , XX.X)]. Mean, standard deviations, median, minimum, maximum, and quartiles will be reported to one decimal place.

Count data will be summarized using median (min, max).

Statistical Modeling and Inferences

Statistical modeling will be performed using linear mixed model for continuous measures and generalized linear mixed model for binary and count outcomes with logit and log link functions, respectively. All models will include site as random effect and intervention arm as a fixed effect. Secondary outcome models will also be adjusted for maternal treatment, stabilization dose, and breast feeding.

For the ith infant, all models (except the primary) will have the following form $g(\mu_i)$ with g(.) being a monotonic link function and the following form:

```
g(\mu_i) = \beta_o + \beta_1 I(\text{intervention=fast}) + \beta_2 I(\text{Maternal Treatment=methadone}) + \beta_3 I(\text{Materna Treatment= Buprenorphine } \pm \text{ naloxone}) + \beta_4 I(\text{Maternal Treatment=other opioids}) + \beta_5 (\text{stabilization dose}) + \beta_6 (\text{Maternal feed=Yes}) + \beta_i X_i
```

where:

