 μ_i = expected value of outcome y_i

 β_0 = intercept, the expected mean number of treatment days when all covariates = 0

 β_1 = Intervention effect of fast vs slow wean interventions

 $\beta_2, \beta_3, \beta_4$ = effect of maternal treatment, compare to no treatment

 β_5 = effect of stabilization dose

 β_5 = effect of breastfeeding

 β_i = effect of the jth covariate added to the model

For normal outcomes, g(.) is the identity link function.

For binary outcomes, g(.) is the logit link function and we will assume that y_i follows Bernoulli distribution. Alternatively, we can follow Zou et al. (2003) and use the natural log function, and we will assume that y_i follows Poisson or negative binomial distribution. Decision will be based on manuscript writing team, if they prefer to report risks vs odd ratios.

For count outcomes, g(.) is the natural log function, and we will assume that y_i either follows Poisson or negative binomial distribution.

All hypothesis tests will be performed using a two-sided significance level of 0.05. Unless otherwise specified, results for each type regression performed will include the following:

- Normal regression
 - Unadjusted
 - Mean (and 95% confidence intervals (CI)) of the outcome in each treatment group.
 - Mean difference (and 95% CI) of the outcome between treatment groups.
 - Adjusted using pre-specified covariates.
 - Mean (and 95% CI) of the outcome in each treatment group.
 - Mean difference (and 95% CI and p-value) of the outcome between treatment groups.
- Logit Binomial regression
 - Unadjusted
 - Rate (and 95% CI) of the outcome in each treatment group
 - Odds Ratios (and 95% CI) of the outcome between treatment groups
 - Adjusted using pre-specified covariates.
 - Rate (and 95% CI) of the outcome in each treatment group
 - Odds Ratios (and 95% CI and p-value) of the outcome between treatment groups.
- Log-Binomial or Poisson regression
 - Unadjusted
 - Risk (and 95% CI) of the outcome in each treatment group
 - Relative risk (and 95% CI and p-value) of the outcome between treatment groups
 - Adjusted using pre-specified covariates.
 - Risk (and 95% CI) of the outcome in each treatment group
 - Relative risk (and 95% CI and p-value) of the outcome between treatment groups.
- Poisson or negative binomial regression
 - Unadjusted
 - Rate (and 95% CI) of the outcome in each treatment group
 - Relative rate (and 95% CI and p-value) of the outcome between treatment groups

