6.5 Bayesian Statistical Methods

6.5.1 Statistical Methods

Due to sample size limitation, the primary outcome (H1) and sensitivity analyses (1) and (2) will be analyzed using Bayesian methods in addition to the frequentist analyses to estimate the posterior distribution for all model parameters. Bayesian models will be fit using Markov chain Monte Carlo methods (MCMC) by using software such as PROC MCMC (SAS) or stan (RSTAN/RSTANARM package in R). Model parameter estimates will be generated by fitting three MCMC chains with randomly drawn starting chain. Each chain will involve 1,000 burn-in iterations and 1,000 additional iterations for each chain. Thinning will be used as necessary to reduce autocorrelation among the samples to produce good sampling of the posterior. Trace plots and Gelman-Rubin convergence diagnostics (Rhat <1.1) for all parameters will be used to monitor convergence. For all models, we will report posterior medians and 95% credible intervals (CrI) for the group difference and the probability that a rapid-wean will reduce the days of opioid treatment, compared to a slow-wean intervention.

Primary outcome (H1)

Linear regression model will be used for the primary outcome with treatment group as fixed effect and as hospital random effect. We will use the following priors:

trt effect ~ Normal (
$$\mu = 0, \sigma = 3$$
)
Intercept ~ Normal ($\mu = 0, \sigma = 10$)

All other covariates ~ Normal ($\mu = 0, \sigma = 2$)

Standard deviation of random effect (hospital) $\sim half - noraml (\mu = 0, \sigma = 1)$

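### The SAP drops both covariates from the protocol's primary model without giving a reason, and no planned analysis fits the protocol model as written

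*SAP*

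**What the plan says.** Protocol 5.1.4 says that the primary regression models "will include the intervention as a fixed effect and will include maternal treatment and stabilization dose as covariates", with hospital as a random effect. It continues: "The primary test of interest will be the F-test of the intervention effect". Protocol 5.1.6 gives the Bayesian primary model the same terms: treatment group, "stabilization dose and maternal treatment as covariates, and we will include hospital as a random effect".

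SAP 4.1 reads: "For the primary outcome (H1), linear mixed model with site as random effect and intervention as a fixed effect will be used". SAP 6.4.1 writes out a covariate-adjusted equation and says that "all models (except the primary) will have the following form". SAP 6.4.3 confines the covariate list to secondary models. For the Bayesian fit, SAP 6.5.1 says: "Linear regression model will be used for the primary outcome with treatment group as fixed effect and as hospital random effect".

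The two covariates return for H1 in sensitivity analysis 1 of SAP 6.4.5, which also adds maternal feeding. SAP 6.5.1 repeats that analysis with Bayesian methods.

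For normal regression, the reporting list in SAP 6.4.1 gives, under unadjusted results, "Mean difference (and 95% CI) of the outcome between treatment groups" and, under adjusted results, "Mean difference (and 95% CI and p-value) of the outcome between treatment groups".

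**The concern.** The headline conclusion depends on one p-value and one confidence interval, and the two documents take them from different models. A reader who holds the published result to the protocol would look for the adjusted F-test. A reader who follows the SAP would look for the intervention-plus-site test. Without a dated reason, nobody outside the trial can tell why one replaced the other.

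The timing adds weight. SAP version 1.0 is dated 31 January 2024, after the 31 December 2023 end date. Nothing in the documents suggests that outcomes by arm had been seen, but a late change to the decisive test is one that a stated reason would protect.

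The change also separates H1 from its own components. SAP 4.1 adjusts H2 and H3, which are the same outcome within morphine and methadone infants. Protocol 5.1.5 had asked for the primary-outcome approach in both. Finally, baseline covariates that predict the outcome would narrow the interval, and the SAP gives this up for H1 when the target had already fallen to 80% power.

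**Working it through.** **1. The models side by side**

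| | Protocol 5.1.4 | SAP 4.1 | SAP sensitivity analysis 1 |
|---|---|---|---|
| Intervention | fixed | fixed | fixed |
| Hospital/site | random | random | random |
| Maternal treatment | yes, coded as in 5.1.3 | no | yes, coded as in SAP 6.4.3 |
| Stabilization dose | yes | no | yes |
| Maternal feeding | no | no | yes |

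The maternal-treatment coding differs in two ways. The protocol's fourth category is non-prescribed opioids; the SAP's is none/unknown. For methadone used with buprenorphine, the protocol classifies by longer use and the SAP by use nearest delivery. So no column of the SAP equals the protocol column.

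**2. Is a reason given?** The SAP revision history lists only missing follow-up data and the Bayley table wording. The opening of SAP 6.4.5 (censoring and partial data) explains why extra analyses are added, not why covariates left the primary model. The clause in SAP 6.4.2 on reducing covariates applies only if convergence fails. A version gap does not explain it either: the SAP cites protocol V10, and the V10-to-V11 log lists face-page changes only.

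**3. The plan's own sample sizes.** Inputs from SAP 3.4: difference 2.0 days, two-sided 0.05, SD 6.9 and then 6.2. Formula: n per arm = 2(z₀.₉₇₅ + z_power)² × SD² / 2.0².

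- SD 6.9, 90%: 2 × (1.960 + 1.282)² × 6.9² / 4 gives 251 per arm, 502 in total.
- SD 6.2, 90%: 202 per arm, 404.
- SD 6.2, 80%: 2 × (1.960 + 0.842)² × 6.2² / 4 gives 151 per arm, 302.

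All three reproduce. They are unadjusted t-test figures, so the model change does not make them wrong.

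**4. Power with and without the covariates, at 151 per arm**

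Unadjusted: noncentrality 2 / (6.2 × √(2/151)) = 2.80 on 300 df; noncentral-t power 79.8%.

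Adjusted: the four covariate terms (three for maternal treatment, one for dose) leave 296 df. Residual SD is 6.2 × √(1 − R²), where R² is the share of variance explained beyond site. Chance imbalance inflates the variance of the treatment effect by about 1 + 4/301 = 1.013. Power was averaged over 4,000 random covariate draws, with assumed maternal-treatment shares of 35/40/5/20%. Three other sets of shares moved it by no more than 0.02 points.

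| Assumed R² | Residual SD | Adjusted power | Change from 79.8% |
|---|---|---|---|
| 0% | 6.20 | 79.3% | −0.5 points |
| 5% | 6.04 | 81.3% | +1.5 |
| 10% | 5.88 | 83.3% | +3.5 |
| 15% | 5.72 | 85.3% | +5.5 |

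Break-even is near R² = 1.3%, which agrees with 1 − 1/1.013.

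**5. How often the two tests disagree.** For each R², 4,000 trials of 302 infants were simulated. They assumed 20 hospitals (protocol 5.3 says that twenty expressed interest), arms balanced within hospital, 10% of variance between hospitals, and hospital in both models. With a true 2.0-day effect, exactly one of the two p-values is at or below 0.05 in 2.3%, 4.5%, 7.1% and 8.6% of trials for R² of 0, 5, 10 and 15%. Repeat runs gave 2.0–2.6%, 4.5–5.3%, 7.0–7.4% and 8.0–8.6%. With no effect, the unadjusted test rejects in 4.5–5.0% and the adjusted test in 4.5–5.1%.

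**The case against.** The SAP is the later and more specific document, is dated before the expected data lock, and names one H1 model consistently. That model is valid and matches the t-test used for sizing. An unadjusted primary analysis with an adjusted sensitivity analysis is a common choice, and readers would see any disagreement between the two. All of this stands. It means that there is no bias and no inflation of error; it does not supply the missing reason.

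The protocol model is not ideal. It fits one dose slope across two drugs, with no drug term. In the appendix examples, morphine stabilization comes to 0.48 mg/kg/day (0.06 × 8 or 0.08 × 6) and methadone to 0.30 (0.1 × 3 or 0.15 × 2), so dose partly stands in for drug. That may limit the precision gained, but a crude baseline covariate leaves the randomized test valid. Protocol 5.1.4 also leaves open whether 35-day exits are counted as 35 days or censored; SAP 6.1.1 settles that, and restoring the covariates need not reopen it.

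The power gain rests on an R² that the documents do not give. Hospital is already in the model, so the increment may be small. The final number of infants is not stated. Disagreement is about 2.3% even when the covariates explain nothing. These figures are therefore illustrative.

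Two lesser points also stand. The p-value list in SAP 6.4.1 is generic and allows exceptions, so it calls only for a clarifying line. And SAP 6.5.1 lists a prior for other covariates under the H1 heading; this may serve sensitivity analysis 1, since the H1 sentence itself names none.

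**Conclusion.** The concern holds and should be fixed. The protocol and SAP name different primary tests for H1, the SAP gives no reason, and the protocol's model is not among the planned analyses. This rests on the text and needs no assumption beyond reading the V10-to-V11 log as complete, so that V10 held the same adjusted model.

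The size is moderate. The cost of adjusting, if the covariates turn out useless, is about half a point of power. The possible gain is about 1.5 to 5.5 points for R² of 5% to 15%, assuming 302 infants, SD 6.2 and complete covariates. The choice of model would change the significance call in roughly one trial in 12 to one in 43 over the R² range of 15% down to 0%. Neither model misstates the type I error.

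**What to change.** **If the data are still blinded:** amend SAP 4.1, 6.4.1 and 6.5.1 so that the H1 p-value and 95% CI come from the protocol model: intervention, maternal treatment, stabilization dose in one stated unit, and random hospital. Use the protocol 5.1.3 coding where the collected data allow it; otherwise state and justify the SAP 6.4.3 coding. Keep a category for unknown exposure so that no infant is dropped. Move the intervention-plus-site model to the sensitivity analyses.

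**If the data are already unblinded:** do not switch. Keep the model that the SAP fixed before lock, disclose the departure from protocol 5.1.4 with its reason and date, and report the protocol model beside it.

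**In either case:** state in SAP 6.4.1 which H1 model carries the p-value.

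The cost is text edits to three SAP sections and some recoding. Two practical points need checking. The protocol's methadone-plus-buprenorphine rule needs duration of use, and the documents do not show that it was recorded. SAP 6.6.1 has no rule for missing in-hospital covariates, so one must be added. First-phase lock was expected by the end of March 2024, so disclosure may be the only route left.

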
 To determine whether a rapid- or slow-wean intervention affects the total amounts of opioid given from the first dose of weaning to cessation of opioid among infants receiving an opioid (defined as morphine or methadone) as the primary treatment for neonatal opioid withdrawal syndrome (NOWS) 	
 The total amount of morphine or methadone given from the first dose of weaning to cessation of opioid

 To determine whether a rapid- or slow-wean intervention affects the administration of second or third line drugs to treat NOWS from the first dose of weaning to cessation of opioid among infants receiving an opioid (defined as morphine or methadone) as the primary treatment for neonatal opioid withdrawal syndrome (NOWS) 	
 Initiation or escalation of second or third line drugs administered to treat NOWS signs from the first dose of weaning to cessation of opioid

 To evaluate the safety and tolerability of a rapid-wean intervention compared with a slow-wean intervention among infants receiving an opioid (defined as morphine or methadone) as the primary treatment for neonatal opioid withdrawal syndrome (NOWS) 	
 Seizures (clinical or EEG), excessive stool output, respiratory disturbances, and feeding tolerance

Objectives	Endpoints
Secondary (cont'd)	

 To determine whether a rapid- or slow-wean intervention affects neurobehavior among infants receiving an opioid (defined as morphine or methadone) as the primary treatment for neonatal opioid withdrawal syndrome (NOWS) 	
 Atypical neurobehavioral profile prior to discharge on the NICU Network Neurobehavioral Scale (NNS) after completion of study drug and prior to hospital discharge

 To determine whether a rapid- or slow-wean intervention affects the total length of hospital stay among infants receiving an opioid (defined as morphine or methadone) as the primary treatment for neonatal opioid withdrawal syndrome (NOWS) 	
 The total number of days spent in the hospital

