5.1.3. Other Collected Data

Initial descriptive analyses will include weaning intervention group characteristics. We will collect data to characterize the following.

- Stratification data
- Hospital variables: participation in ESC
- Maternal variables (e.g., socioeconomic status, obstetric complications, opioid medication, medication assisted treatment program, non-opioid drugs, cigarettes, alcohol, selective serotonin reuptake inhibitors, and psychiatric diagnoses)
- Infant demographics at birth (e.g., gestational age, birth weight, sex, multiples, growth parameters, out-born, and location of care)
- Characteristics of NOWS treatment (e.g., stabilization dose, age at stabilization, use of adjunctive drugs to the primary NOWS drug treatment)
- Infant characteristics at the start of the intervention (e.g., weight, postnatal age) and when medically ready for discharge per the hospital standard.

We will include the stratification variable (hospital) in regression modeling as a random effect, and we will include stabilization dose and maternal treatment as covariates. With respect to maternal treatment, it will be a categorical variable with four categories:

- 1) Methadone use
- 2) Buprenorphine \pm naloxone
- 3) Prescribed opioids other than methadone and buprenorphine \pm naloxone
- 4) Non-prescribed opioids

There will be some mixing among these four groups; therefore, we will use the following rules to classify infants:

- If methadone is used with other opioids, classify as methadone.
- If buprenorphine is used with other opioids, classify as buprenorphine \pm naloxone.
- If methadone is used with buprenorphine, classify based on which drug has been in use for a longer time interval.

Depending on the descriptive comparisons across weaning intervention groups, we may add other variables to the regression models such as medication assisted treatment programs. If the difference of a variable across the weaning intervention is statistically significant at a two-sided alpha of 0.05, then we may include the variable as a covariate in the regression models. Beyond the significant difference, we will consider other factors, such as the type of analysis, correlation with other variables in the model, and trial subcommittee discussion about the nature of the potential covariate.

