We will calculate binomial proportion and their corresponding 95% CI by intervention arm for each of the following safety adverse events: seizures (clinical or EEG), excessive stool output, respiratory disturbances, and feeding tolerance. We will use chi-square tests to compare the proportion of seizures (clinical or EEG), excessive stool output, respiratory disturbances, and feeding tolerances between intervention arms. In addition to unadjusted analyses, we will compare AEs across the weaning interventions by using adjusted logistic regression models that adjust for the stratification variable (hospital), covariates of maternal treatment and stabilization dose, and possibly any baseline variables that were significantly different between weaning interventions. We define covariates that we may adjust for earlier in this section within the paragraph on other collected data.

We will analyze the length of hospital stay in a similar manner as the primary outcome. We will use a simple, unadjusted regression model to analyze the total length of stay and will include a fixed treatment effect (intervention arms). A second regression model will include a fixed treatment effect and will include adjustment for the stratifying variable and covariates of maternal treatment and

stabilization dose. The F-test of the treatment effect will be the primary test of interest. We will report the treatment difference along with 95% CI. Sensitivity analysis will involve time-to-event analyses using survival models to account for skewness and possible censoring of each outcome.

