6.4.3 Covariates

All secondary regression models will include the stratification variable (site) as a random effect and will be adjusted for:

- Breastfeeding status
- Stabilization dose, continuous
- Maternal treatment which will be categorized as follow:
 - Methadone use
 - o Buprenorphine ± naloxone
 - Prescribed opioids other than methadone and buprenorphine ± naloxone
 - o None/Unknown

In case of mixing among the 4 groups the following rules will be followed:

- o If methadone is used with other opioid, classify as methadone
- If buprenorphine is used with other opioid, classify as Buprenorphine ± naloxone
- o If methadone is used with buprenorphine, classify based on which drug has been used most proximal to delivery.

Additionally, if the sample size allows, secondary analyses can be adjusted for critical covariates that are substantially imbalanced at baseline (both clinically and statistically significantly different)

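### Length of stay (H9) counts hospital days before randomisation, and its model omits postnatal age at the start of the intervention, a collected baseline variable that could improve precision at no cost

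*SAP*

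**What the plan says.** Protocol Table 1 (section 1.7) defines the endpoint as "The total number of days spent in the hospital". The SAP (sections 2.2.1 and 6.3) says only length of hospital stay, and does not start the clock at randomisation or at the first weaning dose.

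Protocol 5.1.5 plans two models. For the first: "We will use a simple, unadjusted regression model to analyze the total length of stay". The second "will include adjustment for the stratifying variable and covariates of maternal treatment and" stabilization dose. In SAP 4.1, H9 to H11 "will be analyzed in a similar manner to H2", that is, by a linear mixed model with site as random effect and intervention as fixed effect. The covariates come from the sentence "Secondary outcome models will be adjusted for breastfeeding status, maternal treatment, and stabilization dose"; SAP 6.4.1 and 6.4.3 repeat the list. The only other way in is SAP 6.4.3, which says that, if the sample size allows, "secondary analyses can be adjusted for critical covariates that are substantially imbalanced at baseline", where the imbalance must be both clinical and statistical.

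Protocol 5.1.3 lists among the data collected: "Infant characteristics at the start of the intervention (e.g., weight, postnatal age) and when medically ready for discharge per the hospital standard".

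**The concern.** Infants are randomised after opioid treatment has been started and the dose stabilized. Protocol 4.2.6 leaves that earlier course, including how long stabilization lasts, to each hospital. For an infant born at the study hospital, postnatal age at the first weaning dose is close to the number of hospital days already used. It is therefore nearly a component of total stay. Left out of the model, its variation stays in the residual except for what site and the other covariates pick up.

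The imbalance clause in SAP 6.4.3 does not solve this. It selects covariates by chance imbalance rather than by how well they predict the outcome. Under randomisation a baseline variable reaches significance at 0.05 about one time in twenty, however prognostic it is.

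At stake is the width of the interval for H9. Enrollment was difficult (SAP 3.4 records a target cut from 502 to 302 and then a stop by date), so precision obtainable from data already in hand is worth taking.

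**Working it through.** **The plan's own figures.** SAP 3.4 gives a difference of 2.0 days, SD 6.2, two-sided alpha 0.05 and 80% power. Per arm, n = 2(z₀.₉₇₅ + z₀.₈₀)² SD²/δ² = 2 × (1.960 + 0.842)² × 6.2²/2.0² = 150.9, rounded up to 151, or 302 in total. This matches. The same formula at 90% power gives 404 with SD 6.2 and 502 with SD 6.9, which also match. These figures concern the primary outcome. Neither document states an SD, power or interval width for H9, so there is no H9 figure to reproduce.

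**Set-up for H9 (assumptions).** Write total stay as A + B, where A is days before the first weaning dose (SD s) and B is days after it. Take SD(B) = 6.2, borrowed from the primary outcome; 151 per arm, from the SAP target; and correlation ρ between A and B.

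- Without A in the model: SD = √(6.2² + s² + 2ρ × 6.2 × s)
- With A as a covariate: SD = 6.2 × √(1 − ρ²)
- 95% half-width = t(0.975, 300 df) × SD × √(2/151), with t = 1.968 and √(2/151) = 0.1151

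**No correlation.** With A in the model the half-width is 1.968 × 6.2 × 0.1151 = 1.40 days. Without it (results from unrounded values):

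| s (days) | Share of variance from A | SD of total stay | Half-width (days) | Widening |
|---|---|---|---|---|
| 2 | 4/42.44 = 9% | 6.51 | 1.48 | 5% |
| 3 | 9/47.44 = 19% | 6.89 | 1.56 | 11% |
| 5 | 25/63.44 = 39% | 7.96 | 1.80 | 28% |

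**Allowing for what is already in the model.** If site, stabilization dose and the other covariates absorb half of the variance of A (and none of B), the SD is √(6.2² + s²/2) = 6.36, 6.55 and 7.14. Divided by 6.2, the widening is 3%, 6% and 15%.

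**Allowing for correlation.** With all of the variance of A in the residual again, for s = 2, 3 and 5:

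- ρ = −0.3: SD 5.92, 6.02 and 6.70 without the covariate, 5.91 with it. Widening 0%, 2% and 13%.
- ρ = +0.3: SD 7.06, 7.66 and 9.06 without the covariate, 5.91 with it. Widening 19%, 29% and 53%.

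The percentages are ratios of SDs, so they do not depend on the number finally enrolled, which the documents do not give. The half-widths in days do.

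**The case against.** The case against making much of this is strong on size, and most of it stands.

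- **Precision only.** Randomisation keeps the arm comparison valid with or without the covariate. SAP 6.4.4 calls every analysis other than the primary exploratory, and no precision target is set for H9. Leaving out one more prognostic covariate is a modelling choice, not a mistake.
- **Adjustment already planned.** Differences between hospitals in the pre-weaning course are what the site effect addresses, and stabilization dose may carry part of the rest. Figures that put all of s² in the residual are therefore upper values for a given s when there is no correlation.
- **Direction of correlation.** At ρ = −0.3 the gain almost vanishes for s of 2 to 3 days.
- **Limits set by the design.** Placebo levels in the rapid arm give both arms the same number of study steps when escalations are equal (Protocol 4.2.7 and Appendix 10), and observation of at least 48 hours follows study-drug cessation (Protocol 1.4). Any difference in stay is constrained, whatever the interval width.
- **Age is not always stay.** Out-born infants have spent days elsewhere. In the preparatory chart review 84.0% were in-born (Protocol Appendix 1), so 16% were not.

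A reader might also infer two stronger statements that the documents do not support. One is that they point to a pre-weaning SD near 3 days, because √(6.9² − 6.2²) = 3.0. The 6.9 is the morphine arm of an external trial and runs from opioid initiation, so it omits birth to initiation; the 6.2 is from this trial's infants on either drug. Using the methadone-arm SD of 8.0 instead gives √(8.0² − 6.2²) = 5.1. The other is that H9 is the only outcome bearing on hospital use. H12a to H12c cover later emergency and acute-care visits and hospitalizations, and Protocol 3.3.4 works out its cost saving from treatment days.

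None of this argues against adding the covariate. It limits what can be claimed for it.

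**Conclusion.** The point holds as an opportunity to gain precision. Total stay includes days that the intervention cannot affect, and neither document's H9 model includes the collected baseline variable that most directly measures them. The comparison is not biased, and a reader should not infer that it is.

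The size cannot be fixed from the documents. For pre-weaning SDs of 2 to 5 days, with a post-weaning SD of 6.2 and no correlation, the interval is about 5% to 28% wider than it need be, or about 3% to 15% if half of the pre-weaning variance is already absorbed. Negative correlation can bring this close to nil; positive correlation raises it. This is a free improvement to an exploratory secondary analysis. The primary result does not depend on it.

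**What to change.** In SAP 4.1 and 6.4.3, add one sentence: the H9 model also includes postnatal age at randomisation (or at the start of the intervention) as a fixed, continuous covariate. Keep total stay as the endpoint. State when the stay begins for out-born infants, for example at birth or at admission to the study hospital, so that outcome and covariate share a defined origin.

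As a supportive analysis, report days from the first weaning dose to medical readiness for discharge. This removes the pre-weaning days directly and leaves out any wait after the infant is ready to go, although the documents give no figure for such waits.

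The cost is a few lines in the SAP. Protocol 5.1.3 lists infant characteristics at both time points, so no new data or patients should be needed; confirm that the forms hold the ages or dates. If unblinded H9 results have already been seen, label both additions post hoc.
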